1.2 Study Goals

The long-term goal of this research is to reduce the excess burden of prostate cancer and the morbidity associated with its treatments. The overall objective is to test feasible, effective tools that promote SDM for prostate cancer initial treatment decisions, and which improve those decisions in a manner that is risk-concordant and patient-centered for minority men. Our aim is to test the comparative effectiveness of two kinds of decision aids – during consultation and pre-consultation – alone and in combination to improve patient knowledge, symptom burden, and risk-concordant treatment utilization in localized prostate cancer.

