2.2 Secondary objectives

- 2.2.1** To test the impact of in-visit DA's alone compared to usual care on quality of life outcomes and treatment utilization.
- 2.2.2** To test the impact of out-of-visit DA's alone compared to usual care on quality of life outcomes and treatment utilization.
- 2.2.3** To test the impact of combined in-visit and out-of-visit DA's compared to both usual care and individual DAs on quality of life outcomes and treatment utilization.
- 2.2.4** To test the comparative effectiveness of DA's on minority men's knowledge.
- 2.2.5** To compare clinic time required to administer the DA's across arms.

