4.5 Stratification and Treatment Assignments

While not formal stratification factors, randomization will be set up so that sites will the particular capacities to oversample minority populations will be distributed between the arms, as illustrated in the diagram below.

Grouping Factors/Treatment assignments:

- Arm 1: Pre -and During Consultation Decision Aids
- Arm 2: Pre-Consultation Decision Aid only
- Arm 3: During Consultation Decision Aid only
- Arm 4: Usual Care

5.0**STUDY CALENDAR**

Laboratory and clinical parameters during treatment are to be followed using individual institutional guidelines and the best clinical judgment of the responsible physician. It is expected that patients on this study will be cared for by physicians experienced in the treatment and supportive care of patients on this trial.

Pre-Study Testing Intervals

- To be completed \leq 28 DAYS before registration: History and physical.
- To be completed \leq 90 DAYS before registration: PSA
- To be completed \leq 4 MONTHS before registration: Prostate Biopsy

	Prior to Registration	Baseline*	12 months after baseline**
Test and Observations			
History and Physical	X		
Height	X		
Weight	X		
Prostate biopsy	X		
Chart Review			X(1)
Labs and Staging			
PSA	X		
QOL Instruments			
Baseline Questionnaire		X(2)	
One-year Questionnaire			X(3)

* To be administered following the surgical consultation

** +/- 6 weeks

- 1 At 12 months site staff will review the patient's chart from the 6-month point to the 12-month time-point, collecting treatment information and any pertinent events.
- 2 Includes the Prostate Cancer Treatment Questionnaire and the Decisional Conflict Scale. See Section 10.0 and Appendix I.
- 3 Includes Expanded Prostate Cancer Index Composite (EPIC-26) and the Decisional Regret Scale. See Section 10.0 and Appendix II. To be completed by the patient during a clinic visit. If no clinic visit is scheduled +/- 6 weeks from the 12-month time-point, study staff should mail the 12-month questionnaire with a self-addressed stamped envelope to the patient for him to complete at home and return by mail (see Section 8.3.1).

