8.2.5 Baseline Questionnaire

After consultation with the physician, the study coordinator will escort the patient to a private area preferably near to the patient waiting area, and provide the Baseline Questionnaire for the patient to complete before leaving.

8.3 12-month follow up

Follow up to ascertain the patient's overall and disease specific quality of life and prostate cancer treatment regret will be conducted by site coordinators 12 months (+/- 6 weeks) after the patient's consultation.

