8.3.2 Twelve-month follow-up chart review

At this time site staff will also conduct retrospective chart review to ascertain treatment utilization and complete the follow-up form. Treatment utilization will be categorized by the type of treatment the patient had (surgery vs. radiation vs. active surveillance).

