12.4 Supplementary Analysis Plans

12.4.1 Secondary endpoints

Secondary endpoints will be decisional quality, as measured by the DCS and Decisional Regret; clinical time required; patient QOL, which will be measured by questionnaires and converted into continuous summary scores using standard algorithms; and utilization, which will be categorized by the type of treatment the patient received, as determined by chart review at 12 months post-diagnosis. We will also consider the primary outcome of knowledge within only minority men (pooled) (defined as non-White or Hispanic White), as well as separately within the three racial subgroups. It is worth noting that some patients may receive a follow-up biopsy before these secondary endpoints are measured (at 12 months after first consultation), which could have a strong impact on their DCS and QOL scores. Thus, whether or not a patient receives a follow-up biopsy before 12 months (and the timing of this biopsy) will be taken into account when modeling these endpoints.

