APPENDIX I BASELINE QUESTIONNAIRE BOOKLET

Prostate Cancer Treatment Questionnaire

Please check the TRUE or FALSE box for each statement based on your knowledge of prostate cancer treatments. If you are not completely sure, mark 'Unsure'.

	True	False	Unsure
1. Most prostate cancer spreads quickly to other parts of the body	 1	 2	 3
2. Other illnesses can make treating prostate cancer more difficult	 1	 2	 3
3. Some treatments are better than others at stopping prostate cancer	 1	 2	 3
4. Radiation therapy from a machine for prostate cancer requires weeks of daily treatments	 1	 2	 3
5. Radiation seed therapy for prostate cancer requires weeks of daily treatments	 1	 2	 3
6. Radiation for prostate cancer can cause rectal pain	 1	 2	 3
7. Surgery for prostate cancer can cause urine leakage	 1	 2	 3
8. For most men, radiation therapy for prostate cancer has no effect on urinary control	 1	 2	 3
9. Both surgery and radiation can decrease sexual function	 1	 2	 3
10. Low-risk prostate cancer can be safely monitored	 1	 2	 3
11. After prostate cancer surgery, a man will go home with a catheter	 1	 2	 3
12. Hot flashes is a side-effect of hormone treatment	 1	 2	 3

Investigator developed.

Decisional Conflict Scale*My difficulty in making this choice***A. Which treatment option do you prefer? Please check one.**

- Surgery
- Radiation (includes Brachytherapy, IMRT, proton beam)
- Active Surveillance (also called watchful waiting)
- Unsure

B. Considering the option you preferred, please answer the following questions:

	Yes	Unsure	No

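### The utilization endpoint has no rule for men with more than one treatment or none of the three listed, and its month 6 to 12 chart review can miss the initial decision

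*Combined protocol and SAP*

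**What the plan says.** Section 1.2 sets the overall objective as to "test feasible, effective tools that promote SDM for prostate cancer initial treatment decisions". Secondary objectives 2.2.1 to 2.2.3 then name utilization as an outcome; the first reads "To test the impact of in-visit DA's alone compared to usual care on quality of life outcomes and treatment utilization".

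The endpoint is defined in two places. Section 8.3.2: "Treatment utilization will be categorized by the type of treatment the patient had (surgery vs. radiation vs. active surveillance". Section 12.4.1: "utilization, which will be categorized by the type of treatment the patient received, as determined by chart review at 12 months post-diagnosis". Section 12.4.2 adds a generalized linear mixed model with a fixed effect for each aid and a random site intercept. It gives no link function, reference category or coding rule.

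The period to be reviewed appears only in note 1 of the study calendar (5.0), where staff review the chart "from the 6-month point to the 12-month time-point, collecting treatment information and any pertinent events". Section 8.3 times the follow-up at "12 months (+/- 6 weeks) after the patient's consultation".

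Immediately after the visit, Appendix I asks each man "Which treatment option do you prefer? Please check one", with surgery, radiation, active surveillance and unsure as answers. The answer is not named as an endpoint.

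**The concern.** The aids act at one consultation, on the first choice of management. The endpoint that is meant to show their effect on treatment is worded as what the man had or received by a date a year later. For a man with one treatment the two agree. For a man who starts surveillance and then has surgery, or has surgery followed by radiation, they do not, and the plan does not say which counts. A man on hormone treatment alone, or with nothing started, fits none of the three types, although eligibility extends to T3 disease and Gleason 10.

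The background section itself says that surveillance may only delay treatment, and 12.4.1 foresees that some men may have a follow-up biopsy within the year. The plan therefore anticipates the setting in which categories change.

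At stake is whether the results for objectives 2.2.1 to 2.2.3 on utilization can be interpreted. Staff at 20 sites would each settle the question for themselves, and all patients at a site are in the same arm.

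**Working it through.** The documents give no rate, power or sample size for utilization, so there is no figure of the plan's to reproduce. The check is a comparison of texts, followed by an illustration under stated assumptions.

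**Possible courses set against the texts** (the courses are hypothetical)

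| Course after the consultation | First strategy | Type received by 12 months (8.3.2, 12.4.1) | Treatment events within months 6 to 12 (5.0, note 1) |
|---|---|---|---|
| Surgery in month 2, nothing later | Surgery | Surgery | None |
| Surveillance, then surgery in month 9 | Surveillance | Two types, no rule | Surgery |
| Surgery in month 2, radiation in month 8 | Surgery | Two types, no rule | Radiation only |
| Hormone treatment alone, or nothing started | Other, or none yet | No category | No category |

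The first and third rows show the effect of the calendar window: the first strategy falls outside it, while a later treatment falls inside it. Neither 8.3.2 nor 12.4.1 states such a limit, so the three places need to be reconciled.

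**How many men the coding rule could move**

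Inputs: N = 172 (12.2.2). The share starting surveillance, s, and the share of those converting by 12 months, c, are not in the documents. The assumed ranges are s = 20-50% and c = 5-20%.

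Men whose category depends on the rule = N × s × c:
- low: 172 × 0.20 × 0.05 = 1.7
- middle: 172 × 0.35 × 0.10 = 6.0
- high: 172 × 0.50 × 0.20 = 17.2

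That is about 2 to 17 men, or s × c = 1 to 10 percentage points. It counts only men converting from surveillance, not those with combined, other or no treatment.

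**Direction**

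Suppose converters are coded by their later treatment. With initial surveillance of 35% without an aid and 50% with it (assumed), the true difference is 15 points. The difference observed is 0.50 × (1 − c with aid) − 0.35 × (1 − c without aid):
- 10% in both groups: 0.450 − 0.315 = 13.5 points
- 20% with the aid, 10% without: 0.400 − 0.315 = 8.5 points
- 5% with the aid, 20% without: 0.475 − 0.280 = 19.5 points

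So the difference can shrink or grow. If sites code the first strategy instead, it stays at 15.

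**Site coding and arm**

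With 20 sites in a balanced 2 × 2 design, each aid is compared as 20 / 2 = 10 sites against 10. Coding habits could fall unevenly between the two sets. The random site intercept allows for variation between sites, but it cannot separate a coding habit from the effect of the aid to which the site was assigned.

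**The case against.** The strongest reply is that treatment received over 12 months is a legitimate quantity. The objectives say utilization, and 1.2 also lists risk-concordant utilization among the aims. This stands: the plan may study treatment received. It does not say that it has chosen this over the initial decision, and either choice needs a rule for men with two types.

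Second, the follow-up form is not among the documents and may record dates and sequence. A reader might infer that the initial choice is lost and that the three types are strictly exclusive. The documents do not show this; exclusivity is inferred from the singular wording and the contrast between the three types. A form that holds the dates would make the repair easier, but it would not supply the missing rule.

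Third, 12.4.1 says that a follow-up biopsy and its timing will be taken into account in modelling. That is an adjustment; it does not assign a category.

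Fourth, a reader might infer a conflict of up to about 4.5 months between follow-up from diagnosis and from the consultation (biopsy up to 4 months before registration, visit up to 14 days after it). The documents do not support that as a real difference in follow-up. Sections 8.3 and 5.0, and 12.4.1 itself later in the same paragraph, all place the measurement 12 months after the consultation or the baseline that follows it. One phrase in 12.4.1 is loose.

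Finally, utilization is an unpowered secondary endpoint. That limits the weight of the point but not its validity.

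**Conclusion.** The point holds as a gap in the definition of a secondary endpoint, together with a chart-review window that does not fit it. The plan aims at the initial decision, defines utilization as treatment received by 12 months, gives no rule for men with several types or none of the three, and in 5.0 looks only at the second half of the year.

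A reader might go further and conclude that an aid which moves men toward surveillance will look weaker than it is. The documents do not support that. It requires converters to be coded by their later treatment and conversion to be similar across arms or higher with the aid; neither is stated, and the illustration shows that the bias can run the other way. Nor do the documents say why men convert.

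The range of about 2 to 17 of 172 men rests wholly on the assumed surveillance and conversion shares. The true size and direction are unknown. The primary endpoint is untouched. The change is worth making because it is cheap and loses no information.

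**What to change.** - **8.3.2, 12.4.1 and the follow-up form:** define utilization as the first management strategy adopted after the study consultation, with its start date. Categories: surgery, radiation, active surveillance, other or combined, none yet.
- **Same places:** record any later change and its date as a separate item, so that treatment received by 12 months can also be reported.
- **5.0, note 1:** have the chart review cover the whole period from the consultation to 12 months.
- **12.4.1:** replace the one reference to time since diagnosis with time since the consultation, in line with 8.3, 5.0 and the rest of 12.4.1.
- **Optional:** report the Appendix I part A preference descriptively. It is already collected, but it is a preference rather than utilization and need not become another tested outcome.

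The cost is wording in three sections and the form, and a chart review that also reads the first six months. There is no added burden on patients. The downside is small categories that may need pooling before the mixed model is fitted.

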9.0 ADVERSE EVENTS

We do not anticipate any additional adverse events related to participation in this study beyond usual care. If patients experience any emotional discomfort when completing the questionnaires, they may choose not to complete them and/or speak with the site staff. Patients experiencing any physical or psychological complications related to their standard of care treatment should discuss this with their treating physician.

10.0 MEASURES

10.1 Prostate Cancer Treatment Questionnaire (knowledge measure)

“The Prostate Cancer Treatment Questionnaire” is a 12-item instrument measuring respondent knowledge of key information deemed by clinicians to be critical for patients to successfully deliberate about preference of treatment for prostate cancer.

The questionnaire will be administered once, immediately after the consultation (post-consultation) and should take no more than 5-6 minutes to complete.”

10.2 Decisional Conflict Scale (DCS)

The decisional conflict scale was developed and validated by O'Connor⁷² as an instrument intended to “elicit 1) health-care consumers' uncertainty in making a health-related decision; 2) the factors contributing to the uncertainty; and 3) health-care consumers' perceived effective decision making”. The low literacy version of this questionnaire will be used, and it contains 10 items answered on a 3 point scale (i.e., “yes,” “unsure,” “no”) and may be adapted to specific health-care decision scenarios. Example questions include agreement with the following statements: “Did you know which options were available to you?” “Did you know the benefit of each option?” “Did you feel sure about what to choose?”.

The questionnaire will be administered once, immediately after the consultation (post-consultation). It is estimated that it will take participants approximately 5-7 minutes to complete this questionnaire.

10.3 Expanded Prostate Cancer Index Composite Short Form (EPIC-26)

The Expanded Prostate Cancer Index Composite⁶⁶ measures health-related quality of life and returns summary scores for urinary, bowel, sexual, and hormonal domains with high test-retest reliability and internal consistency.

The questionnaire will be administered once; 12 months after the patient's initial consultation. The instrument contains 26 items, and will take approximately 10-15 minutes to complete.

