Our in-visit tool, Prostate Choice, is a decision aid for PCa treatment that incorporates the best available evidence in a literacy-sensitive, easy to use format for patients and providers delivered on a tablet device. Prostate Choice has a modular format that covers the key components critical to a high quality treatment decision for localized PCa. It personalizes each patient's PCa risk severity using evidence-based prediction tools,^{16,17,58-65} and assesses pretreatment QOL using a validated instrument and elicits the importance of each dimension (urinary incontinence, erectile function) into the treatment decision.⁶⁶ It also reviews all treatment options for localized PCa, including surgery, radiation therapy and active surveillance, as well as estimates of treatment benefit for a reduction in PCa-specific mortality.¹⁰ Moreover, it elicits patient preferences by enabling assignment of relative importance of different dimensions of QOL and disease control; it estimates each patient's overall life expectancy using Medicare life tables⁶⁷ (a strategy endorsed by clinical guidelines).^{4,67} Upon completion of all modules, Prostate Choice provides a one page detailed summary, which can also be printed or emailed, as the foundation for future definitive treatment decisions incorporating individually tailored evidence-based risks, QOL and preferences as well as potential QOL implications regarding treatment.

Prostate Choice was developed with patients, physicians, and designers with experience in informed decision-making. In 2011 with the assistance of the Prostate Cancer Patient Advocate Core of the Mayo Clinic Prostate SPORE, [name], MPH and [name] developed a tablet-based "app" to walk patients through the main categories of concern in early prostate cancer treatment. It is a touch-based interactive user experience that focuses on categories "Your Diagnosis," "Your Situation," "Your Priorities," "Your Treatments," and culminates in a summary combining all the categories. Each of the elements of Prostate Choice can be selected by patient or clinician. It is light on text, but shows numbers and elicits values to help facilitate a better conversation. It has been user-tested and found feasible and acceptable by patients and providers. Moreover, it has been further refined to ensure that it is at a Flesch-Kincaid 8th grade reading level. It conforms to basic decision aid quality criteria.⁶⁸

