Hence, randomization will be conducted at the participating site level instead of patient level. Participating sites will be randomized to one of the four arms. AA-oriented and AI/AN-oriented practices will be those capable of oversampling two of the three the minority populations we are targeting. Randomization will be designed in such a way that AA-oriented and AI/AN-oriented sites are distributed equally to the four arms of the study to prevent, as much as possible, one minority population from being recruited exclusively in only one or two of the intervention arms.

Recruitment: The greatest limitation to accrual feasibility is identifying AI/AN men with newly diagnosed, localized prostate cancer. National data suggest that conservatively 125 cases of prostate cancer occur annually among self-identified Native American men from the Northern Plains and Alaska.¹⁷ We can identify 80% of those men (N = ~100), and approach 80% of them to participate per year (N = 80). We anticipate conservatively that because our intervention is a non-therapeutic

intervention limited to the office visit, 40% of eligible men at participating sites could enroll (n=40 per year for three years) in the Northern Plains and Alaska combined (this is a conservative estimate—most Mayo Clinic decision aid trials accrue 70% of patients approached). We have access to several urban sites from which to draw African American and Hispanic/Latino men, making their recruitment less difficult. The long term success of this line of research will hinge on decision aids being successfully used and their having a positive impact on patient knowledge and risk-concordant treatment decision making. Because of less geographic clustering, men of Hispanic/Latino ethnicity will be recruited from all study sites with a similar overall accrual target, reserving two slots minimum for them during the first year of accrual.

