Thus, the denominator of our test statistic should actually be $[(4\sigma^2/n)(1 + (m-1)\rho)]^{(1/2)}$. Therefore, if we replace the original sample size ($n=100$) with $n(1 + (m-1)\rho) = 100*1.4 = 140$ in the denominator of our original test statistic, we will have a test statistic which accounts for the correlation of 0.1 between subjects within each of the 20 sites. Hence, we will target an effective sample size of 140 patients (approximately 35 patients per arm, 7 patients per site). The total sample size may be further inflated by 20% to account for ineligible, cancel and loss to follow-up for longer term secondary outcomes and allow increased power to detect racial/ethnic differences. Therefore, a total number of 172 patients will be enrolled into this clinical trial. These 172 patients, recruited from 20 participating sites (about 9 patients per site) will receive the intervention (or control) to which their location is randomized.

Though we have chosen to power this study based on an absolute meaningful difference of 8%, we determined the necessary sample size for a range of meaningful differences. In each case, the target power was approximately 85% (thought it varied slightly, as we only considered sizes which were divisible by 20, given the number of expected sites) with joint main effect two-sided t-tests with two-sided alternatives at the 2.5% significance level. These sample sizes are as follows (not adjusted for ineligibility, cancel and loss to follow-up):

Meaningful Difference	Total sample size without correlation within sites	Total sample size adjusted for correlation within sites
4%	360	504
6%	180	252
8%	100	140
10%	60	84
12%	40	56

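### EPIC-26 is collected only at 12 months, so the quality-of-life comparisons can be neither checked nor adjusted for function before treatment

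*Combined protocol and SAP*

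**What the plan says.** Section 10.3 on EPIC-26: "The questionnaire will be administered once; 12 months after" the first consultation. The Study Calendar (Section 5.0) agrees. Its note on the baseline booklet reads "Includes the Prostate Cancer Treatment Questionnaire and the Decisional Conflict Scale", and its note on the one-year booklet reads "Includes Expanded Prostate Cancer Index Composite (EPIC-26) and the Decisional Regret Scale". Appendix I contains no item on function.

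Objectives 2.2.1 and 2.2.2 each test one kind of decision aid "alone compared to usual care on quality of life outcomes and treatment utilization". Objective 2.2.3 does the same for the combination.

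On design, Section 1.5 states: "Participating sites will be randomized to one of the four arms". Section 12.2.2 plans 172 men from 20 sites.

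On analysis, four places matter:
- Section 12.4.2 gives the quality-of-life model fixed effects for the two decision aids and a random site intercept.
- Section 12.4.1 adds that a follow-up biopsy before 12 months will be taken into account.
- Section 12.2.1 permits race, ethnicity, disease severity and site characteristics as optional covariates, and extends a similar approach to the secondary endpoints.
- Section 12.2 defends a single post-intervention measurement, for knowledge only, on three grounds: randomization, learning effects and respondent burden.

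Pre-treatment function does appear inside one intervention. Prostate Choice "assesses pretreatment QOL using a validated instrument" (Section 1.4), but only two arms use it, and those answers are not listed as study data.

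**The concern.** Urinary and sexual function a year after the consultation can be expected to depend partly on function before treatment. Where the baseline score is available, it is usually the most useful covariate for such an outcome. Here it is absent from every arm, and the optional covariates do not replace it.

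Two things are at stake. The first is precision: with 20 sites, the arms can differ noticeably in starting function by chance, and nothing in the model can take that out. The second is a check on who was enrolled. Section 12.3.1 acknowledges that recruitment is not blinded to site, and Section 8.0 lets registration follow the consultation and the Baseline Questionnaire on the same day. If enrolment differed by arm in a way related to function, the data could not show it.

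Of the three grounds in Section 12.2, the learning effect does not apply to self-reported function.

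**Working it through.** **1. The plan's own figures.** The documents give no power, SD or intra-site correlation (ICC) for EPIC-26. For knowledge they give a difference of 8 points, SD 12, two-sided 2.5% and 100 men. A two-sample t-test with 50 v 50 then has 85.3% power, which matches the stated figure of about 85%. The design effect is 1 + (5 − 1) × 0.1 = 1.4, and 100 × 1.4 = 140, as stated. The ICC of 0.1 used below is that knowledge value. Applying it to function is an assumption.

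**2. Chance imbalance in mean baseline function.** With 172 men and 20 sites, m = 172/20 = 8.6 men per site. A factorial main effect compares k = 10 with 10 sites (86 v 86 men). A single-arm comparison as in objectives 2.2.1 and 2.2.2 compares 5 with 5 sites (43 v 43 men). In patient-SD units:

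SE = √{2 × [1 + (m − 1) × ICC] / (k × m)}

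At ICC 0.1 the design effect is 1 + 7.6 × 0.1 = 1.76.
- Main effect: √(2 × 1.76/86) = 0.202, and 1.96 × 0.202 = 0.40.
- Arm v arm: √(2 × 1.76/43) = 0.286, and 1.96 × 0.286 = 0.56.

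| Assumed ICC | 95% range, 10 v 10 sites | 95% range, 5 v 5 sites |
|---|---|---|
| 0 | ±0.30 SD | ±0.42 SD |
| 0.01 | ±0.31 SD | ±0.44 SD |
| 0.05 | ±0.35 SD | ±0.50 SD |
| 0.1 | ±0.40 SD | ±0.56 SD |

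With 140 men (7 per site) and ICC 0.1 the ranges are ±0.42 and ±0.59 SD.

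**3. How much reaches 12 months.** Let r be the correlation between baseline and 12-month scores. The documents do not give it; I assume 0.4 to 0.6. The part of the imbalance carried forward is r times its size.
- Main effect: 0.4 × 0.40 = 0.16 to 0.6 × 0.40 = 0.24 SD.
- Arm v arm: 0.4 × 0.56 = 0.22 to 0.6 × 0.56 = 0.34 SD.

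**4. What adjustment would gain.** If r is similar within and between sites, residual variance is multiplied by 1 − r². That is 1 − 0.16 = 0.84 to 1 − 0.36 = 0.64, a cut of 16 to 36%.

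**5. Detectable difference.** Assume ICC 0.1, 20% loss by 12 months (6.88 men per site), 80% power and two-sided 5%, with t quantiles on 17 degrees of freedom (10 v 10) or 8 (5 v 5). Without a baseline, the detectable difference is 0.64 SD for 10 v 10 sites and 0.97 SD for 5 v 5. At r = 0.5 these become 0.55 and 0.84 SD.

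**The case against.** The strongest reply is that randomization already does the work. It balances function in expectation, and the random site intercept puts chance differences between sites into the standard error. That stands. A reader might infer that a quality-of-life difference could not be told apart from pre-treatment function, or that the test is invalid. The documents do not support either inference. Randomization, as a ground in Section 12.2, carries over to EPIC-26, and so in part does burden. What randomization of sites does not cover is selective enrolment once a site knows its arm.

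Three other readings also go too far:
- *That the model excludes patient covariates.* Section 12.2.1 makes several optional and Section 12.4.1 adds follow-up biopsy. The accurate statement is that none of the optional ones is fixed in advance and none is baseline function.
- *That having few sites explains the imbalance.* At ICC 0 the ranges are already ±0.30 and ±0.42 SD, about three quarters of the values at ICC 0.1. Most of it is ordinary sampling with this many men. The modelled contrast is also 10 v 10 sites, not 5 v 5.
- *That the variance cut equals 1/(1 − r²), or 19 to 56%, more patients.* That would hold only if sites were added in proportion. With 20 sites fixed and ICC 0.1, the variance of a site mean is 0.1 + 0.9/m. Matching the cut would take about 250 to 580 men, so no simple patient equivalent should be quoted.

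**Conclusion.** The point holds as a matter of precision and checking on a secondary endpoint. The primary knowledge analysis is unaffected. The documents are clear that function before treatment is not collected as study data in any arm, so the comparisons in objectives 2.2.1 to 2.2.3 can be neither checked nor adjusted for it.

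Its size rests on two assumptions that the documents cannot settle: the ICC for function and the baseline to 12-month correlation. Within the ranges shown, the share of chance imbalance reaching the modelled 12-month contrasts is moderate. It is larger for the single-arm comparisons named in the objectives, where even with adjustment at r = 0.5 only a difference of about 0.84 SD is detectable. Baseline items would therefore help without making those comparisons well powered. The change is worth making because it is cheap.

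**What to change.** 1. Collect the ten EPIC-26 incontinence and sexual items (Appendix II questions 1 to 3, 4a, and 8a to 12) at baseline in all four arms. Adjust the matching 12-month domain scores for them in the mixed model.
2. Give them before the consultation where consent timing and workflow allow. Otherwise place them after the knowledge test and the Decisional Conflict Scale in the post-consultation booklet. In that case, state that the answers come after the decision aid and after the diagnostic biopsy, because Prostate Choice draws attention to function in two arms only. Use one timing at all sites if possible, and record it.
3. Include center type as a fixed effect in the quality-of-life models. Section 4.3 makes it the randomization stratum. Section 4.5 says the grouping is not a formal stratification factor, so that wording should be aligned.
4. If baseline items are not added, label the quality-of-life contrasts exploratory.

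Cost: ten of 26 items, at the protocol's 10 to 15 minutes for the whole form, is 10/26 × 10 = 3.8 to 10/26 × 15 = 5.8 minutes, so about 4 to 6 minutes per man. A revised booklet and data form are also needed. Asking before the visit may cue the conversation in the usual-care arm. The bowel, hormonal and urinary irritative domains would still have no baseline. The center-type term needs only a change of analysis wording.
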